6.2 IMPORTANT PROTOCOL DEVIATIONS

Handling of iPDS in analysis is included in the DV domain specifications and stored within the TMF in EDMS.

A protocol deviation (PD) is important if it affects the rights or safety of the study subjects, or if it can potentially influence the primary outcome measurement(s) in a non-negligible way. Refer to Identify and Manage Important Protocol Deviations (iPD) (7).

The documentation of the iPD categories and how to handle iPDS in the analysis are done in the DV domain.

Handling of iPDS in analysis is included in the DV domain specifications and stored within the TMF in EDMS.

6.3 SUBJECT SETS ANALYSED

There are two patient sets defined in this trial:

- Enrolled Set (ES)

[figure not shown]
This patient set includes all patients who signed the informed consent form and were also enrolled, regardless whether the patient was treated with trial medication or not.

[figure not shown]
- Treated Set (TS)

The TS includes all patients in the ES who received at least 1 dose of trial medication and is based on the actual treatment received at enrollment visit

The ES will be used for patient disposition.

The TS will be used for demographics, baseline characteristics, treatment exposure, analyses of all efficacy endpoints and safety analyses (including adverse events, laboratory measurements, vital signs, and ECG).

6.5 POOLING OF CENTRES

This section is not applicable because centre/country is not included in the statistical model.

6.6 HANDLING OF MISSING DATA AND OUTLIERS

Every effort should be made to collect complete data at all visits.

With respect to safety evaluations, it is not planned to impute missing values.

6.6.1 Efficacy data

An observed case analysis will be performed for the primary analysis of the secondary outcomes PASI 50, PASI 75, PASI 90, PASI100, and sPGA clear or almost clear endpoints at week 24.

For the secondary outcome time to loss of PASI50/PASI75/PASI90/PASI100 for patients who achieve the response up to Week 288, patients who do not have the PASI assessment performed at a visit and maintained the PASI response at all scheduled visits prior to the missing visit will be treated as censored at the day after the last visit where the PASI response was attained.

For the secondary outcome time to loss of sPGA clear or almost clear for patients who achieve the response up to Week 288, patients who do not have the sPGA assessment performed at a visit and maintained the sPGA response at all scheduled visits prior to the missing visit will be treated as censored at the day after the last visit where the sPGA response was attained.

For the secondary outcome time to loss of sPGA clear for patients who achieve the response up to Week 288, patients who do not have the sPGA assessment performed at a visit and maintained the sPGA response at all scheduled visits prior to the missing visit will be treated as censored at the day after the last visit where the sPGA response was attained.

[REDACTED]

[REDACTED]

[REDACTED]

If at any time a patient uses an inappropriate concomitant medication, then all future data will be excluded for binary variables and for continuous variables and will not be implemented beyond the date of the prohibited medication..

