Contact IRT	X	X	Х	X	X	X	X	Х	X	X	Х		
Dispense study medication	X	X	X	Х	X	X	X	Х	X	X			
Collect study medication	X	X	X	Х	X	X	X	Х	X	X	х		
PASI, sPGA	X	X	X	X	X	X	X	X	X	X	X		
Columbia-Suicide Severity Rating Scale (C-SSRS) ⁷	X	x	x	x	x	x	x	x	x	x	x	X	
Safety laboratory samples	X	X	Х	X	X	X	X	X	X	X	X		
Biomarker samples (serum)											Х		
Whole blood (PBMC)													
for flow cytometry											X		
(pre-dose) ⁸													

Page 8 of 84

Trial Periods		Open Label Treatment										Follow-Up
Visit	15	16	17	18	19	20	21	22	23	24	EOT^{12}	\mathbf{EOO}^{11}
Week	168	180	192	204	216	228	240	252	264	276	288	292
Visit window (days)	±7	±7	±7	±7	±7	±7	±7	±7	±7	±7	±7	+7
Termination of trial medication											X	
Trial completion ^{10, 11}												X
Vital status collection ¹³												X

Boehringer Ingelheim 06 Oct 2020

Clinical Trial Protocol Page 9 of 84

Proprietary confidential information © 2020 Boehringer Ingelheim International GmbH or one or more of its affiliated companies

Flow Chart Footnotes:

Visit 1 will occur on the same day as End of Treatment (EOT) Visit in 1407-0030. Weight, vital signs, physical exam, ECG, pregnancy test, PASI, sPGA,

, C-SSRS, biomarker samples, whole blood

(PBMC) for flow cytometry and are performed only once on that day as part of the EOT Visit in 1407-0030. Visit 1 may be delayed up to 16 weeks if necessary for administrative reasons. If Visit 1 is delayed, these procedures will be done at Visit 1, except for PK, Biomarker and flow cytometry samples.

² Safety laboratory samples will be taken twice in the same day as part of both the EOT Visit in 1407-0030 and for Visit 1 in 1407-0005. Visit 1 collection is only for the following laboratory tests that are not assessed at EOT in study 1407-0030: infection testing, glycosylated Hbc, LDL-cholesterol/HDL-cholesterol, cholesterol total, and triglycerides. If Visit 1 is delayed, then a sample will be taken at Visit 1 to include all tests included in the two samples and only one sample will be taken at EOT for 1407-0030.

³For patients entering from Part 1 of trial 1407-0030, Visit 2.1 is a phone visit, with only adverse events and concomitant medication collected. Visits 1.1, 1.2 and 1.3 do not apply. For patients entering from Part 2 of trial 1407-0030, Visits 1.1, 1.2 and 1.3 to be performed at the clinic with all procedures indicated, Visit 2.1 does not apply.

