Patients with the targeted BI 730357 indications may be at greater risk of cardiovascular disease and associated risk factors, comorbidities in which the likelihood of severe illness from COVID-19 may be increased. Patients with evidence of a current or previous disease or medical condition (other than the target indication) that is clinically significant in the opinion of the investigator are excluded from participation in all trials with BI 730357. To prioritize the safety of patients, in areas with significant COVID-19 morbidity, remote visits will be permitted as needed to replace onsite patient visits in these trials. To ensure that patients may safely continue to participate in the clinical trial, remote visits will require, at a minimum, investigator assessment of new and ongoing adverse events, concomitant therapies, and patient compliance with the trial protocol and

Page 24 of 84

study drug. The BI trial team will remain in close contact with the investigator during the execution of a remote visit.

Trial conduct and protocol-defined procedures do not impose additional risk to trial participants. To address potential risks associated with operational aspects related to the participation in clinical trials in the context of the COVID-19 pandemic, different risk mitigation measures are considered, based on local requirements and development of the pandemic.

Recruitment of clinical trials will proceed when it is considered safe to do so in accordance with local public health guidance.

c22181693-04 Clinical Trial Protocol Page 25 of 84

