3.3.2 Inclusion criteria

1. WOCBP¹ must be ready and able to use highly effective methods of birth control per ICH M3 (R2) that result in a low failure rate of less than 1% per year when used consistently and correctly from date of screening until 4 weeks after last treatment in this trial. A list of contraception methods meeting these criteria is provided in the patient information.

(¹ A woman is considered of childbearing potential (WOCBP), i.e. fertile, following menarche and until becoming post-menopausal unless permanently sterile.

Permanent sterilisation methods include hysterectomy, bilateral salpingectomy and bilateral oophorectomy. Tubal ligation is NOT a method of permanent sterilisation.

A postmenopausal state is defined as no menses for 12 months without an alternative medical cause.)

- 2. Patients with moderate-to-severe plaque PsO who have completed treatment in the preceding trial without early discontinuation, agree to continue treatment in 1407-0005, and
- for patients entering from Part 1 of trial 1407-0030

Page 30 of 84

- o achieve a ≥PASI50 response upon completing the trial 1407-0030 Week 24 end-of-treatment visit
- for patients entering from Part 2 of trial 1407-0030
 - o achieve a ≥PASI50 response upon completing the trial 1407-0030 Week 12 endof-treatment visit or perceived patient improvement, at the discretion of the Investigator
- 3. Signed and dated written informed consent in accordance with ICH-GCP and local legislation prior to admission to the trial.

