Descriptive statistics of the percentage of patients who achieve sPGA of clear (sPGA score of 0 ("clear ")) at Week 24 will be tabulated for each treatment group. The number of patients, number of patients attaining the sPGA response, percentage of patients attaining the sPGA response at Week 24 with corresponding exact 95% confidence interval will be presented based on the Clopper Pearson method.

The primary analysis of these secondary outcomes will be based on an observed case analysis.

Secondary Outcome Time to Loss of PASI50/PASI75/PASI90/PASI100 for patients who achieve the response up to Week 288

For the time to loss of response (PASI 50/ PASI 75/ PASI 90/ PASI 100) the time to event will be calculated as

- Time to first loss (with observed event) = [date of first loss] – [date of first visit with qualifying response] + 1
- Time to first loss (censored) = [date of last visit with qualifying response] – [date of first visit with qualifying response] + 1
- If a patient never attains PASI 50/ PASI 75/PASI 90/PASI 100 then the patient will not contribute to the analysis of this outcome.

Time to loss of response will be analysed descriptively by Kaplan Meier curves. If at least 50% of patients lose response, the median time to loss of response will be estimated median of time to loss with 95% confidence interval will be presented.

Secondary Outcome Time to Loss of sPGA clear or almost clear at Week 24 for patients who achieve the response up to Week 288

For the time to loss of response (sPGA clear or almost clear), the time to event will be calculated as:

- Time to first loss (with observed event) = [date of first loss] – [date of first visit with qualifying response] + 1
- Time to first loss (censored) = [date of last visit with qualifying response] – [date of first visit with qualifying response] + 1
- If a patient never attains sPGA clear or almost clear then the patient will not contribute to the analysis of this outcome.

[figure not shown]
Time to loss of response will be analysed descriptively by Kaplan Meier curves. If at least 50% of patients lose response, the median time to loss of response will be estimated median of time to loss with 95% confidence interval will be presented.

Secondary Outcome Time to Loss of sPGA clear at Week 24 for patients who achieve the response up to Week 288

For the time to loss of response (sPGA clear), the time to event will be calculated as:

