- Time to first loss (with observed event) = [date of first loss] – [date of first visit with qualifying response] + 1
- Time to first loss (censored) = [date of last visit with qualifying response] – [date of first visit with qualifying response] + 1
- If a patient never attains sPGA clear then the patient will not contribute to the analysis of this outcome.

Time to loss of response will be analysed descriptively by Kaplan Meier curves. If at least 50% of patients lose response the median time to loss of response will be estimated median of time to loss with 95% confidence interval will be presented.

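### SAP 6.6.1 and 7.5.2 treat a loss of response seen after a missed visit differently, and the median condition, read literally, can suppress an estimable Kaplan-Meier median

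*SAP*

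**What the plan says.** Time to loss of PASI50/75/90/100, of sPGA clear or almost clear, and of sPGA clear are secondary endpoints, described by Kaplan-Meier curves with no hypothesis test (Protocol 7.2; SAP 7.5.2).

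- **Missed assessments, SAP 6.6.1.** A patient without a PASI assessment at a visit who "maintained the PASI response at all scheduled visits prior to the missing visit will be treated as censored at the day after the last visit" with response. The two sPGA endpoints have the same rule. Later assessments are not mentioned.
- **Time formulas, SAP 7.5.2.** For events: "Time to first loss (with observed event) = [date of first loss"], minus the date of the first qualifying visit, plus 1. For censored patients: "Time to first loss (censored) = [date of last visit with qualifying response"], minus the same date, plus 1. Missed visits are not mentioned.
- **Median, SAP 7.5.2.** "If at least 50% of patients lose response, the median time to loss of response will be estimated". The sPGA clear paragraph repeats the condition.
- **Week 24 response, SAP 6.6.1 and 7.5.2.** The main analysis is observed case. SAP 7 has a general rule that categorical percentages use everyone in the patient set, including those with missing values.

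**The concern.** Section 6.6.1 can be read as closing a patient's follow-up at the first gap, even when the next visit shows that response has been lost. Section 7.5.2 can be read as counting that loss. Two programmers following the SAP could therefore report different event counts and times for the same patients.

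Gaps are foreseeable. SAP Table 6.7: 1 schedules 24 assessments after Day 1, from Week 12 to Week 288 at 12-week intervals. Protocol 1.4 and 6.1 allow remote visits, and "remote visits will require, at a minimum, investigator assessment of new and ongoing adverse events, concomitant therapies, and patient compliance with the trial protocol" and study drug. PASI and sPGA are not in that minimum.

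The median condition adds to this. Under censoring, the share of patients seen to lose response is not the quantity that decides whether a Kaplan-Meier median exists. Censoring at the first gap lowers that share further.

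**Working it through.** The documents give no event count, loss rate, dropout rate or missed-visit rate for these endpoints, so there is no planned figure to reproduce. All rates below are assumptions.

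**One patient, both rules** (nominal days from SAP Table 6.7: 1). Response is first seen at Day 84 and again at Day 168; Day 252 is missed; response is absent at Day 336. Prior visits are taken as those since response was first attained.
- 6.6.1 sets status: censored, 168 − 84 + 1 = 85 days.
- 7.5.2 alone: event, 336 − 84 + 1 = 253 days.

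PASI50 in Part 1 needs no such reading of prior visits. Entry requires a "PASI50 response upon completing the trial 1407-0030 Week 24 end-of-treatment visit", and "Visit 1 will occur on the same day as End of Treatment (EOT) Visit in 1407-0030". If Visit 1 counts as the first qualifying visit, response at Days 1, 84 and 168 with the same gap and loss gives censoring at 168 − 1 + 1 = 168 days, or an event at 336 − 1 + 1 = 336 days.

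If response resumes after the gap (Day 336) and is lost at Day 420, 7.5.2 gives an event at 420 − 84 + 1 = 337 days. Section 6.6.1 gives censoring at 85 days or at 336 − 84 + 1 = 253 days, depending on which visit is taken as the last with response.

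**Events lost if 6.6.1 governs.** Simulation: 120 responders, exponential loss with true median 120 weeks, visits every 12 weeks, administrative censoring uniform over Weeks 96–288, misses independent of disease state. True Week 96 retention is 0.5^(96/120) = 57.4%.

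| Missed per visit | Losses, first-miss censoring | Losses, across gap | Week 96 retention, first-miss / across | SE in points, first-miss / across |
|---|---|---|---|---|
| 0% | 76.9 | 76.9 | 57.4% / 57.4% | 4.5 / 4.5 |
| 2% | 66.8 | 76.7 | 57.5% / 57.5% | 4.7 / 4.5 |
| 5% | 55.1 | 76.6 | 57.3% / 57.6% | 5.1 / 4.5 |
| 10% | 40.9 | 76.5 | 57.5% / 57.9% | 5.9 / 4.5 |

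The fall in losses is 10.1/76.9 = 13%, 21.8/76.9 = 28% and 36.0/76.9 = 47%. A separate simulation (90 responders, 3–5% loss and 2–5% dropout per visit) gave 15–17%, 30–35% and 48–57%.

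**Median condition.** Ten responders: losses at Weeks 12, 36, 60 and 84; censoring at Weeks 24, 48, 72, 96, 108 and 120. The numbers at risk at the losses are 10, 8, 6 and 4, so the curve at Week 84 is (9/10)(7/8)(5/6)(3/4) = 0.492. The median is estimable at Week 84, but only 4/10 = 40% lost response, so the literal condition withholds it. The reverse fault did not appear: in 10,855 random datasets with a crude share of at least 50%, none lacked a Kaplan-Meier median.

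How often this happens depends on unknown rates. With 40 responders, true median 120 weeks and the same censoring, an estimable median is withheld in 2% of runs with no misses, in 60% at 5% missed with first-miss censoring, and in 2% at 5% missed when follow-up crosses gaps. With no misses but censoring spread over Weeks 12–288, the figure is 35%.

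**Week 24 denominator.** With an assumed 9 of 90 missing and 57 responders, observed case gives 57/81 = 70.4% and the full set 57/90 = 63.3%.

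**The case against.** The strongest reply is that the two sections are complementary. Section 6.6.1 is the missing-data section and decides who is censored; 7.5.2 supplies times once status is known, and its plus 1 matches the day-after wording. That reading is coherent and may be what was meant. It removes the conflict, but only by settling on the rule that discards losses the trial has observed. It also has to be inferred, because no precedence is stated.

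A second reply is that the rule does little harm. For the curve this stands: with random misses, Week 96 retention barely moves and the cost is precision. Following patients across gaps is not free either. A loss during the gap is dated at the next assessed visit, which raises Week 96 retention by about half a point at 10% missed (57.9% against 57.4%).

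On the median, the condition follows directly on the sentence about Kaplan-Meier curves, so the curve may be what is meant. The text speaks of patients, however, and does not say so.

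Four stronger readings might be inferred, and the documents do not support them:
- *Most patients would be affected.* The chance of at least one miss in 24 assessments is 1 − (1 − p)^24 = 38%, 71% or 92% at p = 2, 5 or 10%. This applies only to someone responding from Day 1, followed through every assessment and never losing response. A miss after a loss is irrelevant.
- *The SAP contradicts itself on the Week 24 denominator.* Observed case is stated for each Week 24 endpoint in 7.5.2, and a general tabulation rule yields to it.
- *Observed case inflates Week 24 response because patients stopping for worsening drop out.* SAP 6.7 allocates on-treatment end-of-treatment values of early stoppers to windows, so one from Days 126–209 counts at Week 24. Earlier stoppers remain absent, but redacted text may hold a supportive analysis.
- *The sentence on inappropriate concomitant medication is a defect.* Adjacent text is redacted and the deviation specifications cited in SAP 6.2 are not visible. Limiting the exclusion to psoriasis drugs would be debatable, since Protocol 1.4 describes the drug as a sensitive CYP3A substrate.

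**Conclusion.** The point holds for the descriptive time-to-loss endpoints. The same patient can be censored at 85 days or an event at 253 days, and no sentence decides between them. If 6.6.1 governs, about 13%, 28% or 47% of recorded losses are discarded at an assumed 2, 5 or 10% missed per visit, and the standard error of Week 96 retention rises from 4.5 to 4.7, 5.1 or 5.9 points. A claim of biased curves is not supported: if misses are random there is almost no bias. If misses tracked worsening disease the answer would differ, but the documents give no basis for sizing that.

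The median condition, read as a crude share, can only suppress a median. The ten-patient example shows this without any assumed rate; its frequency in this trial is unknown. The Week 24 denominator needs no more than a clarifying clause.

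No hypothesis is tested and the curves are shown either way. This should be corrected, but it does not threaten the trial's main conclusion.

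**What to change.** 1. In SAP 6.6.1, let follow-up continue across a missed visit to the next assessed PASI or sPGA. Censor at the last visit with response only when no later assessment exists. Cross-refer to 7.5.2 so that both sections give one status and one time, and note that a loss during a gap is dated at the next assessed visit.
2. In SAP 7.5.2, report the median whenever the Kaplan-Meier estimate reaches 0.5 or below, and otherwise state *not reached*. Add retention estimates at fixed times.
3. Minor: add one clause stating that the observed-case denominator at Week 24 is an exception to the general percentage rule in SAP 7. Add a supportive Week 24 table, counting antipsoriatic rescue or discontinuation for worsening as non-response, only if the redacted text does not already contain one.

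The first two items and the clause are wording changes that need no new data. The optional table would use the reason for stopping and the rescue therapy, which Protocol 3.3.4.1 and 4.2.1 already require to be recorded.

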4.2 OTHER TREATMENTS, EMERGENCY PROCEDURES, RESTRICTIONS

4.2.1 Other treatments and emergency procedures

Stable doses of concomitant therapies for chronic conditions, for which neither the condition nor the treatment are judged to exclude the patient from participation (cf. Section 3.3) may be permissible. All concomitant medications should be carefully evaluated by the Investigator and the Clinical Monitor Local (CML) should be contacted when there are questions regarding concomitant medications.

In the event that a patient experiences an intolerable increase of PsO during the course of the trial, the trial medication will be discontinued and anti-psoriatic agents may be used as rescue medications. Refer to Section 6.2.3 for early treatment and trial termination instructions.

In case of any AEs in need of treatment, symptomatic therapy according to investigator judgment will be permitted. All concomitant and/or rescue therapies will be recorded on the appropriate pages of the electronic case report form (eCRF).

Severe infections according to RCTC grading, serious infections, and opportunistic or mycobacterial infections:

Treatment of the infection should be initiated promptly according to local standard of care. Treatment with trial medication should be discontinued.

Clinical Trial Protocol Page 38 of 84

Malignancies

c22181693-04

In case of occurrence of malignant neoplasm other than appropriately treated basal cell carcinoma or squamous cell carcinoma of the skin or in situ carcinoma of uterine cervix, the investigator should discontinue treatment with the trial medication, and notify the CML. Diagnostics and treatment should be initiated according to local standard of care.

Suicidality

In case of signals of suicidal ideation the patient should be referred to a mental health professional for further work-up.

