4.2.2 Restrictions

4.2.2.1 Restrictions regarding concomitant treatment

The medications, classes of medications, and foods listed in Table 4.2.2.1: 1 must not be taken for the time periods as specified. Classes of antipsoriatic medications listed in Table 4.2.2.1: 1 are likewise restricted, however may be permitted as rescue treatment, at the Investigator's discretion, if a patient experiences an intolerable increase of PsO during the course of the trial and the patient is undergoing early treatment and trial termination. In such cases, the Investigator must notify the BI CML and document the details of the drug used and reason in the eCRF. A comprehensive list of restricted medications can be found in the ISF.

Page 39 of 84

Table 4.2.2.1: 1 Restricted antipsoriatic medications, concomitant treatments and food

Medication or class of medications	Specified restriction time	
Drugs with known phototoxic or photoallergic potential (e.g., tetracyclines, fluorchinolones)	One week prior to randomisation in preceding study until EOO in this study	
Drugs or foods (e.g., seville oranges, grapefruit, paw paw and their products) which are known inhibitors or moderate or strong inducers of CYP3A, or are sensitive substrates of CYP1A2 CYP2B6, or CYP2C8, CYP2C9, or CYP2C19.	One week prior to randomisation in preceding study until EOO in this study	
Drugs with narrow therapeutic windows which are substrates of P-gp, BCRP, OATP1B1, OATP1B3, OAT3, OCT2, MATE1, and MATE2-K	One week prior to randomisation in preceding study through EOO in this study	
Investigational device or product (other than antipsoriatic drugs)	30 days prior to randomisationin preceding study through EOO in this study	
Any drug known to interfere with or to aggravate PsO including but not limited to lithium and interferons	4 weeks prior to randomisation in preceding study through EOO in this study	
BCG (Bacillus Calmette-Guérin) vaccine	1 year prior to randomisation in preceding study through 1 year after last administration of study drug in this study	
Investigational antipsoriatic drugs	12 weeks prior to randomisation in preceding study through EOO in this study	
Systemic anti-psoriatic medications or phototherapy	12 weeks prior to randomisation in preceding through EOO in this study	

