7. PLANNED ANALYSIS

The format of the listings and tables will follow the standards defined in the BI corporate guideline “Reporting of clinical trials and project summaries” .

The individual values of all patients will be listed, sorted by treatment, patient number and visit. The listings will be included in Appendix 16.2 of the CTR.

For EoT tables, the set of summary statistics is: N / Mean / SD / Min / Median / Max.

For appendix tables, the set of summary statistics is: N / Mean / SD / Min / Q1 (lower quartile) / Median / Q3 (upper quartile) / Max.

Tabulations of frequencies for categorical data will include all possible categories and will display the number of observations in a category as well as the percentage (%) relative to the respective treatment group. Percentages will be rounded to one decimal place. The category “missing” will be displayed only if there are actually missing values. Percentages will be based on all patients in the respective patient set no matter whether they have non-missing values or not.

No interim analysis is planned for this trial.

For patients from Part 1 of the 1407-0030 trial planned treatment for first 12 weeks of treatment is defined as treatment patient received at the end of 1407-0030. Planned treatment for after 12 weeks (Period 2) is defined as the treatment patient assigned from IVRS at week 12 visit (V2). For patients who titrate according to the protocol from 100 g *q.d.* dose to 200 g *q.d.* dose, if the investigator determines that the patient may benefit from the higher dose, 200 g *q.d.* dose will be the planned dose after the titration.

Subject data listings of data used in the analyses (i.e. demographic and baseline characteristics and key efficacy endpoints) will also be provided and included in Appendix 16.2 of the CTR.

Disposition of the patient population participating in the trial will be summarised by presentation of the frequency of patients screened, entered, screened but not entered, treated, entered but not treated. Within treated patients, data for patients rolled over from Part 1 of trial 1407-00030 will be summarized by treatment periods (period 1 - first 12 weeks of treatment and period 2 – open label treatment after week 12) for treatment ongoing patients, patients complete planned treatment period and patients who are prematurely discontinued, by reason.

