7.5 SECONDARY ENDPOINT(S)

7.5.1 Key secondary endpoint(s)

This section is not applicable as no key secondary endpoint has been specified in the protocol.

7.5.2 (Other) Secondary endpoint(s)

For the convenience of writing and reviewing, all PASI and sPGA endpoints at different time points (secondary and further clinical endpoints) are first described generally in this section prior to addressing each secondary objective specifically.

Psoriasis Area and Severity Index (PASI)

Details for scoring Psoriasis Area and Severity Index (PASI) and its components are described in Section 10.1 of the CTP. The percent reduction from baseline is calculated by % PASI reduction from baseline = $((\text{PASI at baseline} - \text{PASI at Visit X}) / \text{PASI at baseline}) * 100$, at all visits with PASI collected. Achieving an X% or larger reduction from baseline PASI score is denoted as PASI X.

Static Physician's Global Assessment (sPGA)

The sPGA is scored using the following levels of assessment:

0 - clear 1 - almost clear 2 - mild 3 - moderate 4 - severe

Secondary Outcome Achievement of PASI50/PASI75/PASI90/PASI100 at Week 24

Descriptive statistics of the percentage of patients who achieve a PASI score of at least 50% (PASI 50), 75% (PASI 75), 90% (PASI90) and 100% (PASI100) reductions from baseline at Week 24 will be tabulated for each treatment group. The number of patients, number of patients attaining the PASI response, percentage of patients attaining the PASI response at Week 24 with corresponding exact 95% confidence interval will be presented based on the Clopper Pearson method.

The primary analysis of these secondary outcomes will be based on an observed case analysis.

Secondary Outcome Achievement of sPGA clear or almost clear at Week 24

Descriptive statistics of the percentage of patients who achieve sPGA of clear or almost clear (sPGA score of 0 or 1 ("clear or almost clear")) at Week 24 will be tabulated for each treatment group. The number of patients, number of patients attaining the sPGA response, percentage of patients attaining the sPGA response at Week 24 with corresponding exact 95% confidence interval will be presented based on the Clopper Pearson method.

The primary analysis of these secondary outcomes will be based on an observed case analysis.

Secondary Outcome Achievement of sPGA clear at Week 24

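### Patients rescued for worsening psoriasis can drop out of the Week 24 response rate and be censored in time to loss, instead of counting as failures

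*SAP*

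**What the plan says.** **Data after medication.** SAP 6.6.1 says: "If at any time a patient uses an inappropriate concomitant medication, then all future data will be excluded for binary variables". The sentence extends to continuous variables and ends unclearly: something "will not be implemented beyond the date of the prohibited medication". No visible text assigns a non-response value.

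**Week 24 response.** SAP 7.5.2 repeats for each PASI and sPGA response endpoint: "The primary analysis of these secondary outcomes will be based on an observed case analysis". The general rule in SAP 7 points the other way: "Percentages will be based on all patients in the respective patient set no matter whether they have non-missing values or not".

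**Time to loss.** Under SAP 6.6.1, a patient in response at every visit before a missed PASI assessment "will be treated as censored at the day after the last visit where the PASI response was attained"; sPGA has the matching rule. SAP 7.5.2 gives the formula that begins "Time to first loss (censored) = [date of last visit with qualifying response". No visible rule makes the start of a medication a loss.

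**Rescue.** Under Protocol 4.2.1, when psoriasis increases intolerably, "the trial medication will be discontinued and anti-psoriatic agents may be used as rescue medications". Protocol 4.2.2.1 says that the anti-psoriatic classes in the restricted table "are likewise restricted, however may be permitted as rescue treatment", for a patient who is also undergoing early treatment and trial termination. Rescue agents are therefore restricted medications, and the SAP 6.6.1 rule on inappropriate or prohibited medication reaches them.

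**The concern.** Rescue for an intolerable increase of psoriasis marks treatment failure. Setting aside PASI and sPGA values obtained under rescue is sensible, because improvement caused by another drug should not be credited to BI 730357. The difficulty is that nothing replaces those values. The failure is not carried into the analysis, so whether a patient stays in the estimate depends partly on the outcome being estimated. For time to loss, this makes the censoring informative.

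Long-term efficacy is part of the main objective (Protocol 2.1.1), and SAP 6.1 reports time to loss by dose group (100, 200 and 400 mg). If rescue is more frequent in one group, that group's figures are flattered more, which distorts even an informal comparison between doses.

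**Working it through.** The documents give no response rate, loss rate or rescue rate, so there is no plan figure to reproduce. The check traces what happens to a rescued patient and then illustrates the size with assumed inputs.

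**1. Route at Week 24.** PASI and sPGA are scheduled every 12 weeks (Flow Chart), with none at Visits 1.1 to 1.3 or at EOO. A patient who stops early has an EOT visit as soon as possible and an EOO visit 4 weeks after the last dose (Protocol 6.2.3). EOT is thus the last scheduled PASI. SAP Table 6.7: 1 places an early EOT value in the Week 24 window only if it falls on Days 126 to 209; on Days 2 to 125 it belongs to Week 12.
- EOT before Day 126: there is no Week 24 value, whatever the timing of rescue. The observed-case rule removes the patient.
- EOT on Days 126 to 209, before the medication: the value is used, and a non-response counts.
- EOT on Days 126 to 209, after the medication: SAP 6.6.1 excludes the value, and the patient leaves the rate.

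**2. Size at Week 24.** N = 90 is the approximate maximum from Part 2 (Protocol 3.1). Assumed: 70% response among patients with a value, m rescued patients without a usable value, and no other missing data. With x responders, the observed-case rate is x/(N − m) and the failure-counted rate is x/N. The gap equals the observed-case rate times m/N.

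| Rescued (m) | Observed case | Counted as failure | Gap |
|---|---|---|---|
| about 5% (4) | 60/86 = 69.8% | 60/90 = 66.7% | 3.1 points |
| 10% (9) | 57/81 = 70.4% | 57/90 = 63.3% | 7.0 points |
| 20% (18) | 50/72 = 69.4% | 50/90 = 55.6% | 13.9 points |

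Holding the failure-counted rate at 63/90 = 70.0% instead, observed case gives 63/86 = 73.3%, 63/81 = 77.8% and 63/72 = 87.5%. The direction is the same.

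**3. Route in time to loss.** A loss seen at a scheduled visit or at EOT before the medication is an event. If the medication comes first, the exclusion leaves no later usable assessment, and the missing-visit rule then censors the patient around the last response visit. This combines two rules; SAP 6.6.1 does not name time-to-event variables in the exclusion sentence.

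**4. Size in time to loss.** Assumed: loss probability h = 5% per 12-week interval, with a share f of losses medicated before being recorded. With every loss counted, the Kaplan-Meier factor per interval is 1 − h. With the share f censored, it is 1 − h(1 − f)/(1 − hf). Ninety-six weeks is eight intervals.

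| f | Factor | Still in response at 96 weeks | Median |
|---|---|---|---|
| 0 (all counted) | 0.9500 | 66.3% | 168 weeks |
| 10% | 0.9548 | 69.1% | 180 weeks |
| 25% | 0.9620 | 73.4% | 216 weeks |
| 50% | 0.9744 | 81.2% | not reached by 288 weeks |

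The upward shift at 96 weeks is about 3, 7 and 15 points.

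**The case against.** **The exclusion sentence is not the main cause at Week 24.** Permitted rescue comes only with early termination, so at most one scheduled PASI (EOT) is left for the sentence to remove. Without it, most patients rescued before Week 24 would still be missing from an observed-case analysis. This stands, so the fix must address the observed-case handling as well as the exclusion.

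**Many failures are still counted.** A reader might infer that treatment failures as a class leave the estimates. The documents do not support that: losses recorded at a visit or at EOT before the medication remain in both analyses. Only failures without such a record escape.

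**The SAP may already keep these patients in the denominator.** Applied literally, the all-patients rule in SAP 7 would in effect count them as non-responders. The endpoint-specific observed-case rule is the narrower one and probably governs, but the two conflict and the SAP does not settle it.

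**Text is redacted.** Three blocks directly before the exclusion sentence are redacted. A reader might infer that no non-responder rule or sensitivity analysis exists; that cannot be established. The visible sentence and the stated primary handling stand regardless.

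**The stakes are limited.** The endpoints are secondary and descriptive, there is no hypothesis testing (Protocol 7.2), and the primary safety endpoint is untouched. At 63/90 the exact 95% interval is 59.4% to 79.2%, so a 3-point shift lies well inside sampling error. This limits the weight of the point, but a bias in a known direction is not reduced by a wide interval.

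**Conclusion.** The concern holds in a limited form. On the visible text, a patient who stops trial drug and is rescued for worsening psoriasis before a usable Week 24 value drops out of the Week 24 rate. If no loss was recorded before the medication, the patient is, on the natural reading, censored in time to loss. Both effects bias the estimates upward.

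The size is unknown. About 3, 7 and 14 points at Week 24 rest on an assumed 70% response and assumed rescue shares of 5%, 10% and 20% in 90 patients. The time-to-loss shifts rest on an assumed 5% loss per interval and an assumed share of unrecorded losses. None of these rates is in the documents, so the larger values should not be read as expected ones. Nor does the SAP say expressly that an EOT PASI taken after rescue is deleted from time to loss; that is an inference. If SAP 7 governs the denominator, the Week 24 part disappears and the time-to-loss part remains.

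**What to change.** Amend SAP 6.6.1 and 7.5.2:
- (a) A patient who starts a restricted anti-psoriatic medication because of psoriasis worsening or lack of effect, with the reason as recorded in the eCRF, before the Week 24 assessment counts as a non-responder and stays in the denominator.
- (b) In time to loss, the start date of that medication is the loss date if no earlier loss was recorded.
- (c) Keep the exclusion rule for prohibited medication taken for other reasons. Show the current observed-case and censoring rule as a sensitivity analysis. Reconcile the Week 24 denominator with the all-patients rule in SAP 7.

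The condition on the reason matters. Protocol Table 4.2.2.1: 1 also restricts systemic corticosteroids and topical treatments for other skin conditions, and their use for unrelated reasons should not become loss of response.

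The cost is SAP wording and one derived flag. Rescue therapies, with drug details and reason, already go into the eCRF (Protocol 4.2.1 and 4.2.2.1), so no new data are needed and neither treatment nor visits change. The downside is slightly less favourable response and durability figures.
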